6.13.8. Renal Safety

To assess renal safety, a summary and analyses using LOCF will be provided for renal functional laboratory measures: estimated glomerular filtration rate (eGFR), Chronic Kidney Disease-Epidemiology Collaboration (CKD-EPI), creatinine, urine albumin/creatinine ratio (ACR), by treatment. The ANOVA model will be fitted with treatment as a fixed effect on the ranked LOCF change from baseline data.

An ANCOVA model will be fitted with treatment as a fixed effect. The change from baseline in rank for each parameter will be the response variable.

The minimum eGFR value and the maximum creatinine, urine ACR will be used for baseline and post baseline calculation to generate the shift table. Within treatment comparison will be tested using generalized McNemar's test. The shift table will use eGFR cutoff (<30 , $30-60$, $60-90$, and ≥ 90 mL/min/1.73m²), creatinine (≤ 1 ULN, >1 and ≤ 2 ULN, >2 and ≤ 4 ULN, and >4 ULN), and UACR (<30 , (≥ 30 and ≤ 300), and >300 mg/g). The overall randomized treatment comparison will be tested using a likelihood-ratio Chi-square test. The shift table for minimum eGFR for both baseline and post-first dose at Week 18 will be classified using the

To examine AE indicating decrease in renal function, the SMQ for acute renal failure and a LSC for chronic renal failure events will be used to search the clinical trial data base for events of interest. A listing will be provided with all detected TEAE from these categories.

6.13.9. Immunogenicity

Summaries dulaglutide anti-drug-antibodies (ADA) will be generated separately for treatment-emergent ADA, for detected ADA by each dulaglutide treatment if more than 3% patients developed an ADA.

The patient treatment-emergent ADA data will be listed.

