## **9.8. Biomarkers and Antibodies**

### **9.8.1. Samples for Immunogenicity Research**

Samples from patients in each treatment arm will be tested for the development of treatment-emergent dulaglutide ADA, defined as 4-fold increase in titer from baseline. A blood sample will be collected at specific study visits according to the Schedule of Activities (Section 2).

Treatment-emergent positive dulaglutide ADA samples will be evaluated for their ability to neutralize the activity of assigned treatment (dulaglutide-neutralizing antibodies). Positive dulaglutide ADA samples may also be tested for cross-reactivity with native GLP-1, and if positive, then for neutralizing antibodies against native GLP-1.

Samples will be retained for a maximum of 15 years after the last patient visit for the study, or for a shorter period if regulations and ERBs impose shorter time limits, at a facility selected by Lilly or its designee. The duration allows the sponsor to respond to future regulatory requests related to dulaglutide.

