
Tertiary/Exploratory (continued)
 
Efficacy
 
 • To compare the investigational dose dulaglutide arms (4.5 mg and 3.0 mg) to the 1.5 mg arm for efficacy measures at 18 weeks 
Safety
 
 • To compare the investigational dose dulaglutide arms (4.5 mg and 3.0 mg) to the placebo arm for additional safety measures at 18 weeks • To compare the investigational dose dulaglutide arms (4.5 mg and 3.0 mg) to the 1.5 mg arm for safety measures at 18 weeks 	
 • Change from baseline in HbA1c • Proportion of patients achieving HbA1c target <7.0% or ≤6.5% • The change in FSG (by central laboratory) from baseline • The change in body weight from baseline • The change in 6-point SMPG profiles from baseline • The change in fasting plasma glucagon from baseline • The change in HOMA-IR and HOMA-%B from baseline • Selected gastrointestinal tolerability AEs (nausea, vomiting, and diarrhea) • Pancreatic safety assessed by incidence of cases of adjudicated pancreatitis • CV safety assessed by the incidence of adjudicated deaths and nonfatal major CV events • Thyroid-related safety assessed by the incidence of cases of thyroid neoplasms • Vital signs (PR, BP) • ECG (HR, QTcF, supraventricular arrhythmias and cardiac conduction abnormalities) • Immune system-related safety, including the incidence of dulaglutide antidrug antibodies (ADA) and the incidence of allergic and hypersensitivity reactions • Injection site reactions • Incidence of rescue therapy initiation due to severe, persistent hyperglycemia • TEAEs and SAEs • Discontinuation of study drug due to AEs • Incidence and rate of hypoglycemia (severe, total, documented symptomatic, and nocturnal) • Selected gastrointestinal tolerability AEs (nausea, vomiting, and diarrhea) • Pancreatic safety assessed by incidence of cases of adjudicated pancreatitis • CV safety assessed by the incidence of adjudicated deaths and nonfatal major CV events

Objectives and Endpoints

Objectives	Endpoints

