Incidence of nausea, vomiting, and diarrhea, vital signs (pulse rate, blood pressure [PR, BP]), electrocardiogram (ECG) variables (heart rate [HR], PR interval, and Fridericia's corrected QT interval [QTcF]), and pancreatic enzyme (amylase and lipase) will be summarized by the randomized treatments, and by algorithm within the same investigational dulaglutide dose, and by algorithm across the investigational dulaglutide doses.

Placebo will serve as the reference treatment for each dulaglutide dose, while dulaglutide 1.5 mg as the active comparator for each investigational dulaglutide dose.

All efficacy and safety data will be summarized by each treatment group at each scheduled visit unless otherwise indicated. A scheduled visit is based on the analysis window for the selected

parameters of interest (Appendix 1, Table APP1.1) not the actual visit number reported by the site. For the other measures, the actual scheduled visit reported by the sites will be used.

A mixed-model repeated measures (MMRM) analysis will be used to analyze continuous longitudinal variables. In this model, restricted maximum likelihood will be used to obtain model estimates with Kenward-Roger (KR) option to estimate denominator degrees of freedom. The corresponding baseline value will be used as a covariate, and the stratification factors (pooled country, HbA1c strata [screening HbA1c at Visit 1: <8.0%, \geq 8.0%]), treatment (dulaglutide 4.5 mg, dulaglutide 3.0 mg, dulaglutide 1.5 mg, placebo), visit, and treatment-by-visit interaction will be fixed effects. For HbA1c change from baseline analysis or HbA1c target analysis, HbA1c strata will be replaced with continuous baseline HbA1c as a covariate from the aforementioned model. An unstructured covariance structure will be used to model the within-patient errors. If this model fails to converge, the following covariance structures will be tested in order:

- toeplitz with heterogeneity
- autoregressive with heterogeneity, by visit
- compound symmetry with heterogeneous variances by visit
- toeplitz
- autoregressive
- compound symmetry without heterogeneous variances, by visit
- compound symmetry

The first covariance structure that converges will be used.

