6.13. Safety Analyses

The safety analyses will include adverse events (AEs), serious adverse events (SAEs), AEs of special interest (AESIs), and treatment emergent adverse events (TEAEs), safety laboratory

analytes, vital signs, ECG. Adverse events of special interest include hypoglycemic and hyperglycemic episodes, pancreatitis, thyroid C-cell hyperplasia and C-cell neoplasms, allergic/hypersensitivity reactions, supraventricular arrhythmias and cardiac conduction disorders.

An AE will be coded using the Medical Dictionary for Regulatory Activities (MedDRA). TEAEs are defined as postbaseline events that are new events or preexisting conditions that worsened in severity after randomization using MedDRA low level term (LLT). The maximum severity level for baseline and post baseline for each same LLT term will be used as a criterion to determine TEAEs. If an AE occurs on the same date as the first dosing date with missing event occurring time, that event will be counted as post baseline event.

Unless otherwise specified, the ITT population will be used for analyses of safety measures, and all randomized population for data listing.

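### SAP 6.13.9 leaves the placebo arm out of at least the detected-ADA table, although Table GBGJ.1 lists ADA incidence as an exploratory endpoint versus placebo

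*SAP*

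**What the plan says.** SAP Table GBGJ.1 has two exploratory safety objectives that list the incidence of dulaglutide ADA as an endpoint: "To compare the investigational dose dulaglutide arms (4.5 mg and 3.0 mg) to the placebo arm for additional safety measures at 18 weeks" and "To compare the investigational dose dulaglutide arms (4.5 mg and 3.0 mg) to the 1.5 mg arm for safety measures at 18 weeks". The Protocol's Table GBGJ.1 carries the same two objectives.

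Protocol 9.8.1 has samples from every treatment arm tested for "treatment-emergent dulaglutide ADA, defined as 4-fold increase in titer from baseline". Protocol 10.3.4.11 promises summaries and listings of ADA and names no arm as excluded.

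SAP 6.13.9 plans summaries "separately for treatment-emergent ADA, for detected ADA by each dulaglutide treatment", on condition that more than 3% of patients developed an ADA. It adds one listing: "The patient treatment-emergent ADA data will be listed". The SAP does not itself define treatment-emergent ADA.

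Two general rules bear on this. SAP 6.1 sets the default grouping: "All efficacy and safety data will be summarized by each treatment group at each scheduled visit unless otherwise indicated". SAP 6.13 sets the populations: "the ITT population will be used for analyses of safety measures, and all randomized population for data listing".

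**The concern.** An ADA rate on dulaglutide is hard to read alone. Some positives come from the assay and some from reactivity that was there before treatment. The placebo arm shows how often such positives occur after baseline in the same laboratory and the same population. This trial collects and tests those samples, and one of its stated objectives is the comparison with placebo. A table that stops at the dulaglutide arms leaves that objective without its comparator. What is at stake is the interpretation of an exploratory safety endpoint for two investigational doses; no efficacy conclusion depends on it.

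**Working it through.** The plan gives no ADA figure to reproduce. The check is mainly a comparison of texts, with some counts to show scale.

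**1. Does the all-arms default rescue the placebo column?** The default in SAP 6.1 gives way wherever a section indicates otherwise. SAP 6.13.9 names dulaglutide treatments. Neighbouring sections refer to each randomized treatment or treatment group: 6.13.4.2 (hyperglycemia), 6.13.4.3 (pancreatitis), 6.13.4.5 (allergic reactions) and 6.13.4.6 (arrhythmias). The narrower phrase therefore displaces the default wherever it applies.

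**2. How far does the phrase reach?** The sentence is not grammatical and allows two readings.

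| | Restriction covers both summaries | Restriction covers detected ADA only |
|---|---|---|
| Treatment-emergent ADA, placebo | listing only | tabulated under the SAP 6.1 default |
| Detected ADA, placebo | not tabulated | not tabulated |

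The second row is the same either way. The one listing in SAP 6.13.9 covers treatment-emergent data, so a placebo patient with detected but not treatment-emergent ADA appears in no output that section plans.

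**3. Which objectives does the table serve?** The comparison of 3.0 mg and 4.5 mg with 1.5 mg can be read from it. The comparison with placebo cannot, for detected ADA on both readings and for treatment-emergent ADA on the broader one.

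**4. How much does the placebo count matter?** Assume 75 evaluable patients per arm (about 75 are randomized per arm, SAP 5.2). SAP 6.1 uses Fisher's exact test unless 80% of cells have an expected count of at least 5. In the cases below, two of the four cells have expected counts of 3 or 3.5, so Fisher applies.

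- 6/75 = 8.0% versus 0/75: p = 2 × C(75,6)/C(150,6) = 0.028.
- 6/75 versus 1/75: p = 2 × [C(75,7) + 75 × C(75,6)]/C(150,7) = 0.116.

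With 0 placebo positives, 6 on a dose are needed for p ≤ 0.05; with 1, 8 are needed. One placebo case changes how the same dulaglutide count reads.

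**5. When is a table produced at all?** The trigger is "for detected ADA by each dulaglutide treatment if more than 3% patients developed an ADA", with no stated denominator. The smallest count above 3% is:

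- one arm: 0.03 × 75 = 2.25, so 3 patients;
- three dulaglutide arms: 0.03 × 225 = 6.75, so 7 patients;
- all arms: 0.03 × 300 = 9, so 10 patients.

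Two positives in one arm (2/75 = 2.7%, exact 95% CI 0.3% to 9.3%) would give no table if the trigger is applied per arm.

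**6. The 4-fold definition.** It is stated only in Protocol 9.8.1. Neither document says what titer, if any, an ADA-negative baseline sample carries, or what happens if the baseline is missing. The documents give no baseline prevalence. If 1% to 10% of patients were positive at baseline (an assumption), 297 to 270 of 300 would be baseline-negative, so the convention would apply to most patients.

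**The case against.** The strongest reply is that the placebo data are not lost. Safety listings use all randomized patients, SAP 6.1 names placebo among the listing groups, and at low counts a reader can count placebo cases by hand. The SAP also allows additional analyses after datalock. The endpoint is exploratory and unpowered: 2/75 against 0/75 gives p = 2 × (75 × 74)/(150 × 149) = 0.50, so a placebo column would not settle a difference that small. The treatment-emergent definition already compares each patient with a Visit 3 sample, which partly deals with pre-existing antibodies. The table does serve the 1.5 mg comparison.

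Most of this stands and limits the point. It does not remove it. The SAP 6.13.9 listing covers treatment-emergent cases only and gives no incidence or denominator, so it does not help with detected ADA. Within-patient baselines do not show how often positives arise after baseline without the drug. An analysis that may be added later is not a planned one.

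Four stronger inferences are tempting, and the documents do not support them.

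- **That the placebo comparison is impossible.** It is unplanned in the table; the samples are tested.
- **That the 4-fold rule cannot classify baseline-negative patients, so that none could be treatment-emergent.** This assumes negative samples carry no numeric titer, and the documents do not say how negatives are reported. What stands is that the definition does not say how to classify them.
- **That new antibodies would be missed.** A negative-to-positive change in a dulaglutide arm would still count in the separate detected-ADA summary, subject to the 3% trigger.
- **That the higher doses are untested.** Protocol 3.2 reports 33 patients treated earlier at 3.0 mg or more.

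**Conclusion.** The point holds in limited form. Followed as written, SAP 6.13.9 omits placebo from the detected-ADA table on either reading, and from the treatment-emergent table on the broader one. The planned tabulation therefore does not serve the exploratory placebo comparison in Table GBGJ.1, although every arm is tested. The consequence is confined to how ADA rates are interpreted. Its practical size depends on background reactivity in placebo, which the documents do not give; the counts in the working are illustrations that assume 75 evaluable patients per arm. The undefined trigger denominator and the silence on negative or missing baselines are matters for clarification. They are not shown to be errors.

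**What to change.** In SAP 6.13.9, change the grouping so that both the treatment-emergent and the detected-ADA summaries cover every randomized treatment, placebo included. Show number positive, number evaluable and percentage, with the comparisons of 3.0 mg and 4.5 mg versus placebo and versus 1.5 mg that Table GBGJ.1 lists.

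In the same edit, as secondary clarifications:

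- state the denominator of the 3% trigger, or drop the trigger for this listed endpoint;
- state how an ADA-negative or missing baseline is handled under the 4-fold titer definition.

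These rules should be settled before unblinding: SAP 7.5.2 has the immunogenicity data arriving about 1 or 2 months after final database lock. The cost is SAP wording and a table column. The placebo samples are already to be tested, and Protocol 10.3.4.11 does not restrict the summaries by arm, so no new data are needed.

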6.13.10. Clinical Laboratory Evaluation

Amylase, lipase, calcitonin, eGFR, creatinine, urine ACR are included in Section 6.13.4.3, Section 6.13.4.4, and Section 6.13.8. For other laboratory safety measurements summaries will be provided in this Section. For continuous (numeric) laboratory analytes, the rank on the change from baseline to endpoint (Week 18) will be analyzed as detailed in Section 6.1. For qualitative laboratory analytes, the number and percentages of patients with normal and abnormal values will be analyzed using Chi-square tests or Fisher's exact test.

A summary report and analysis for treatment-emergent abnormal laboratory values (outside the reference ranges as appropriate) will be provided for each continuous analyte by treatment. Shift tables of the change from baseline value to the maximum post baseline value to Week 18 for selected analytes using clinically meaningful thresholds will be summarized separately using generalized McNemar's test for within-treatment comparison and using likelihood ratio test for between-treatment (randomized) comparisons. A shift table for ALT, AST, ALP, GGT, total bilirubin, and direct bilirubin will be generated using cutoff \leq 1ULN, (> 1 ULN and < 3 ULN), (≥ 3 ULN and < 5 ULN), (≥ 5 ULN and < 8 ULN), ≥ 8 ULN.

Laboratory measurements will be listed by patient. Additional listings will be presented for laboratory measurements that are outside the normal range and for measurements outside certain prespecified clinically relevant thresholds if deemed appropriate. A listing of patients with either AST or ALT ≥ 3 xULN, and total bilirubin ≥ 2 X ULN will also be provided.

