- j A serum pregnancy test will be performed at Visit 1 for women of childbearing potential only.
- k A urine pregnancy test will be performed at Visit 3 with the result available prior to randomization and first injection of study drug for women of childbearing potential only. Additional pregnancy tests may be performed at the investigator's discretion during the study.
- l Follicle-stimulating hormone test performed at Visit 1 for postmenopausal women at least 50 years of age with an intact uterus, not on hormone therapy, and who have had spontaneous amenorrhea for more than 6 months and less than 12 months. After Visit 1, additional tests may be performed at the investigator's discretion during the study.
- m For Visit 3, Visit 6, Visit 10, Visit 12, Visit 801, and the ET visit, patients should be reminded to report to the site in a fasting condition, after a period of approximately 8 hours without eating, drinking (except water), or any significant physical activity and before taking their OAMs (if used).
- n Urinary albumin and creatinine are measured; the ratio is calculated.
- o The CKD-EPI equation will be used by the central laboratory to estimate and report eGFR. Values that are  $<60$  mL/min/1.73 m^2 at Visit 1 must be retested at Visit 2. If the highest of the 2 values is lower than the cutoff value for discontinuation of metformin per country-specific label (for example,  $<45$  mL/min/1.73 m^2 or  $<60$  mL/min/1.73 m^2), the patient will be discontinued from the trial prior to randomization. After randomization (Visit 3), values that are  $<60$  mL/min/1.73 m^2 must be first confirmed on a retest before any protocol-required treatment adjustment is implemented.
- p Collect sample in P800 tube. Aliquot samples, 1 for glucagon and the remainder for nonpharmacogenetic biomarker.
- q PK samples at Visit 3 and Visit 5 should be collected 1-24 hours post-injection of study drug.
- r PK sample at Visit 4 should be collected immediately prior to administration of study drug.
- s PK sample at Visit 6 should be collected 5-7 days (120-168 hours) post-injection of Week 5 study drug or just pre-injection of Visit 6 study drug.
- t PK sample at Visit 10 should be collected 1-4 days (24-96 hours) post-injection of Visit 10 study drug.
- u PK samples at Visit 12, Visit 801, and the ET visit can be collected at any time during the visit.

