#### **9.4.3. Safety Monitoring**

Lilly will periodically review evolving aggregate safety data within the study by appropriate methods, including trends in safety variables, laboratory analytes, and AEs. An AC will review prespecified safety reports in an unblinded fashion. In addition, the study team will review safety reports in a blinded fashion according to the schedule provided in the Trial-Level Safety Review plan. Lilly will also review SAEs within time frames mandated by company procedures. The Lilly CRP will, as appropriate, consult with the functionally independent Global Patient Safety therapeutic area physician or clinical scientist.

In addition, specific safety measures are included in the protocol to ensure appropriate monitoring of pancreatic, thyroid, and liver safety. Laboratory findings that trigger pancreatic and thyroid safety monitoring per Lilly standards are provided in Sections [9.2.2.2](#) and [9.2.2.3](#), respectively. Details of liver safety monitoring are provided in [Appendix 4](#). If a study patient experiences elevated ALT  $\geq 3 \times$  ULN, alkaline phosphatase  $\geq 2 \times$  ULN, or elevated total bilirubin  $\geq 2 \times$  ULN, clinical and laboratory monitoring should be initiated by the investigator per Lilly Hepatic Safety Monitoring Algorithm. Details for hepatic monitoring depend upon the severity and persistence of observed laboratory test abnormalities. To ensure patient safety and comply with regulatory guidance, the investigator is to consult with the Lilly CRP regarding collection of specific recommended clinical information and follow-up laboratory tests. See [Appendix 4](#).

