#### Clinical Chemistry

##### Serum Concentrations of:

Sodium  
 Potassium  
 Total bilirubin  
 Direct bilirubin  
 Alkaline phosphatase  
 Alanine aminotransferase (ALT)  
 Aspartate aminotransferase (AST)  
 Blood urea nitrogen (BUN)  
 Creatinine  
 Creatine kinase (creatine phosphokinase; CPKd)  
 Uric acid  
 Calcium  
 Albumin  
 Glucosee

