## Appendix 4. Hepatic Monitoring Tests for Treatment-Emergent Abnormality

---

Selected tests may be obtained in the event of a treatment-emergent hepatic abnormality and may be required in follow-up with patients in consultation with the Lilly, or its designee, clinical research physician.

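### The liver shift tables in SAP 6.13.10 have no cut between 1 and 3 xULN, so they do not show the protocol's bilirubin and alkaline phosphatase limits, and their GGT row has no scheduled baseline.

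*SAP*

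**What the plan says.** SAP 6.13.10 sets out the liver table: "A shift table for ALT, AST, ALP, GGT, total bilirubin, and direct bilirubin will be generated using cutoff". Five bands follow, common to all six analytes: up to 1, above 1 to below 3, 3 to below 5, 5 to below 8, and 8xULN or more. The second is written as "> 1 ULN and < 3 ULN".

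The same section describes how shift tables are built: "Shift tables of the change from baseline value to the maximum post baseline value to Week 18". It says they are for selected analytes and use thresholds that are clinically meaningful. It plans one listing with named limits: AST or ALT at 3xULN or more together with total bilirubin at 2xULN or more. Further threshold listings are optional and their limits are not named. It also plans a by-treatment summary of treatment-emergent values outside the reference range, a rank analysis of change from baseline, and by-patient listings.

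Protocol 9.4.3 says that at ALT 3xULN, ALP 2xULN or total bilirubin 2xULN and above, "clinical and laboratory monitoring should be initiated by the investigator per Lilly Hepatic Safety Monitoring Algorithm". Protocol 8.1.1 lists conditions for considering discontinuation of study drug. They include total bilirubin above 2xULN (together with raised ALT or AST, or with raised ALP), ALP above 2.5xULN (with raised bilirubin or with symptoms), and ALP above 3xULN alone.

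Protocol Appendix 2 lists the scheduled chemistry panel: total and direct bilirubin, ALP, ALT and AST are there, GGT is not. GGT is listed as a test only in Appendix 4, which opens: "Selected tests may be obtained in the event of a treatment-emergent hepatic abnormality". The Schedule of Activities places the chemistry panel at Visit 1, Visit 12 (Week 18) and early termination.

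**The concern.** The 1/3/5/8 scale fits ALT and AST, whose protocol limits are 3, 5 and 8xULN. Applied to bilirubin and ALP it puts most of the protocol's limits inside one wide band. The SAP elsewhere treats 2xULN as the level of interest for bilirubin (its own listing) and gives creatinine a separate scale with a cut at 2xULN (6.13.8), so analyte-specific bands are already its practice.

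At stake is the by-arm categorical picture of liver chemistry at two doses above the approved range. If the arms differ in how many patients reach a level at which the protocol asks for monitoring, the shift table as specified would not show it. The GGT row is a separate defect: the plan calls for a table whose baseline column has no planned data.

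**Working it through.** The plan states no figure to reproduce. The check places a value on each side of every protocol limit into the SAP bands and asks whether the band changes.

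| Analyte and limit | Source | Values (xULN) | SAP bands | Seen? |
|---|---|---|---|---|
| Total bilirubin, 2 or more | Protocol 9.4.3 | 1.99, 2.0 | both >1 to <3 | no |
| Total bilirubin, above 2 | Protocol 8.1.1 | 2.0, 2.01 | both >1 to <3 | no |
| ALP, 2 or more | Protocol 9.4.3 | 1.99, 2.0 | both >1 to <3 | no |
| ALP, above 2.5 | Protocol 8.1.1 | 2.5, 2.51 | both >1 to <3 | no |
| ALP, above 3 | Protocol 8.1.1 | 2.99, 3.01 | >1 to <3, then 3 to <5 | yes |
| ALT, 3 or more | Protocol 9.4.3 | 2.99, 3.0 | >1 to <3, then 3 to <5 | yes |
| ALT or AST, above 5 | Protocol 8.1.1 | 4.99, 5.01 | 3 to <5, then 5 to <8 | yes |
| ALT or AST, above 8 | Protocol 8.1.1 | 7.99, 8.01 | 5 to <8, then 8 or more | yes |

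For bilirubin and ALP, 4 of the 5 limits are not seen. For ALT and AST, the three limits tested are all seen.

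The effect depends on the baseline value:

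- **Baseline at or below ULN.** A rise to 1.2xULN and a rise to 2.8xULN fall in the same cell. The patient is counted as shifting, but the table cannot say whether 2 or 2.5xULN was reached.
- **Baseline already above ULN.** A move from 1.1 to 2.9xULN stays on the diagonal and counts as no shift, although it crosses 2xULN and, for ALP, 2.5xULN.

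The other outputs in SAP 6.13.10, for isolated bilirubin or ALP:

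- The combined listing needs AST or ALT at 3xULN or more. It therefore omits bilirubin at 2xULN on its own, and it has no ALP criterion. The 8.1.1 condition pairing ALP above 2.5xULN with bilirubin above 2xULN is not captured unless a transaminase is also raised.
- The treatment-emergent abnormal summary is by arm but separates only inside from outside the reference range.
- The rank analysis compares change between arms and has no threshold.
- The by-patient listings hold the raw values, but are not a by-arm count.

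For GGT, a shift needs a baseline and a later value. Scheduled measurements under Appendix 2 and the Schedule of Activities: none at baseline and none at Week 18, so 0 of about 300 randomized patients. Any GGT obtained under Appendix 4 comes after a treatment-emergent abnormality, from patients selected for having one.

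**The case against.** The strongest reply is that nothing here is a contradiction. The limits in protocol 9.4.3 and 8.1.1 govern patient care, and protocol 10.3.4.12 asks only for selected analytes and clinically meaningful thresholds; it does not say that shift bands must mirror monitoring triggers. A patient with a normal baseline who reaches 2xULN does shift. Bilirubin above 2xULN never stands alone in 8.1.1, and its pairing with raised ALT or AST is essentially what the named listing covers. The stand-alone ALP criterion at 3xULN is a cut. An almost empty GGT table would be noticed at programming.

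Most of this is right, and it limits the point. It does not supply a by-arm count at 2 or 2.5xULN, nor a GGT baseline.

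Three stronger readings are tempting, and the documents do not support them:

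- **That isolated bilirubin or ALP changes appear nowhere else, or that these tables are the only by-arm view.** The treatment-emergent summary and rank analysis are by arm, and the patient listings carry every value.
- **That the kidney table has the same fault.** SAP 6.13.8 says: "The shift table will use eGFR cutoff", with cuts at 30, 60 and 90. The study-drug limit in 8.1.1 is 30, and the post-randomization retest in the Schedule of Activities footnote is triggered below 60; both are cuts. The value 45 is an entry limit and an example of a country metformin label. A further eGFR table is mentioned, but its classification is lost where the available text breaks off, so the absence of a 45 cut cannot be asserted. A value of exactly 60 fits two bands as written, which is a notation clean-up only.
- **That direct bilirubin is mis-banded.** The protocol limits name total bilirubin only.

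**Conclusion.** The point holds as a minor, inexpensive improvement to safety reporting; the GGT row is wrong as written. For total bilirubin and ALP, four of five protocol limits lie inside one band, and no named by-arm output shows those crossings. The primary analysis, sample size and alpha are untouched.

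The conclusion rests on two readings. First, the general baseline-to-maximum construction in 6.13.10 applies to the liver table; a baseline-to-Week 18 version would need a baseline just the same. Second, the optional threshold listings do not already use 2 and 2.5xULN, since none are named. The documents do not say how many patients will start above ULN on bilirubin or ALP, so the number of missed shifts cannot be estimated. For GGT the accurate statement is that no measurement is scheduled, not that none will ever exist.

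**What to change.** In SAP 6.13.10:

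- **Total bilirubin:** add a cut at 2xULN, giving up to 1, >1 to <2, 2 to <3, 3 to <5, 5 to <8, and 8 or more.
- **ALP:** add cuts at 2 and 2.5xULN, giving up to 1, >1 to <2, 2 to 2.5, >2.5 to <3, 3 to <5, 5 to <8, and 8 or more.
- **ALT, AST and direct bilirubin:** leave as they are.
- **GGT:** remove it from the shift table and list any values obtained.

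These cuts are the protocol's own limits, used for tabulation; no patient-management rule changes. The cost is SAP text and table shells, with no new data. Cells become slightly sparser: the full grid goes from 5 x 5 = 25 cells to 6 x 6 = 36 for bilirubin and 7 x 7 = 49 for ALP, with about 75 patients per arm. That weakens the planned generalized McNemar and likelihood-ratio tests somewhat for these two analytes.
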